**Table 2: Summary of Clinically Significant Reintervention / Lesion Related Mortality Co-Primary Endpoint**

Outcome	Definition (per Clinical Protocol Section 3.3)	Endpoint Time Evaluated	Final Source Data
Clinically Significant Reintervention			
Clinically-Indicated Condition	An untreated device seal zone endoleak, target-lesion growth (> 5 mm in maximum diameter) or post-treatment TAAA rupture without reintervention at the 12 Month window follow-up visit	12 mo f/u visit	Core Lab (aneurysm size and endoleak) CEC Adjudication (TAAA rupture) Site Data (reintervention)
Device Effectiveness	A compromise of a device seal zone or loss of device integrity (e.g., device kink or collapse) requiring placement of an additional stent or stent-graft	12 mo f/u visit	CEC adjudication
Subject Safety	Total occlusion of a device component, use of a bypass graft or the performance of an open conversion in order to maintain bodily vessel function	12 mo f/u visit	
Complicated Device System Prophylaxis	Any device-related intervention requiring hospitalization, or extension of hospitalization, of three days or more	12 mo f/u visit	
Lesion-related mortality			
Lesion-related mortality	All deaths during hospitalization for index endovascular procedure and within 30 days of the index endovascular procedure or any secondary procedures due to the treated pathology, or the effectiveness of the endovascular repair (e.g., procedures to treat retrograde dissections, losses of patency, losses of device integrity, endoleaks, migrations, aortic expansions, aortic ruptures) and any deaths related to the treated pathology or endovascular graft (e.g., aneurysm rupture, retrograde dissection leading to fatal cardiac tamponade), unless evidence is available to demonstrate that the death is not lesion related	12 mo f/u visit	CEC adjudication

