Conversion to open repair	A reintervention that resulted in explant of the device and open surgical repair*	Through 12 Months	Site
Aortoiliac device limb occlusion	An occlusion in the distal bifurcated component, contra-lateral limb component, contra-iliac extender component, or the ipsi-lateral extender component*	Through 12 Months	Core Lab
Loss of device integrity	Defined as any of the following: 
 
Wire fracture identified in the sealing row stents of either the aortic, branch or iliac components
 
Transient (compression) or permanent stent-graft collapse (invagination) following complete
 
	Through 12 Months	Core Lab

Outcome	Definition	Endpoint Time Evaluated	Final Source Data
	device deployment, resulting in an overall reduction in the aortic, branch or iliac vessel luminal diameter		
Primary patency Adapted Study Definition	Blood flow without occlusion maintained through the device after implant without an intervention.	Through 12 Months	Site and Core Lab
Assisted primary patency Adapted Study Definition	Blood flow maintained through the device after implant regardless of re-interventions performed (without occlusion)	Through 12 Months	Site and Core Lab
Secondary patency Adapted Study Definition	Blood flow through the device regardless of reinterventions performed (with or without occlusion) and freedom from surgical bypass	Through 12 Months	Site and Core Lab
All reinterventions	An additional unanticipated interventional or surgical procedure (including conversion to open surgery), related to the device (including withdrawal of the delivery system) or procedure. Anticipated or unanticipated status will be determined at the discretion of the investigator.  These will not include unanticipated, corrective intervention at the access site(s), or device intervention to address non-treatment area issues	Through 12 Months	Site
Branch Vessel Device Effectiveness Measures			
Branch vessel patency	Primary, Assisted Primary, Secondary Patency	12 Months	Site and Core Lab
Acute kidney injury	>50% decrease in eGFR within 30 days of TAMBE Device treatment when compared to pre-treatment serum creatinine value	30 days	Site
Renal function deterioration	A sustained >25% decrease in eGFR over two consecutive study visits following TAMBE Device treatment when compared to pre-treatment serum creatinine value	12 Months	Site

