2.6 Sample Size Calculations

Sample size calculations were determined using PASS 13.0.8 (“Tests for One Proportion using Proportions” and “Exact” options).

The sample size calculation was motivated primarily by the Clinically Significant Reintervention Hypothesis / Lesion Related Mortality, since that would require more subjects to properly power than the Uncomplicated Technical Success / Procedural Safety hypothesis.

At least 86 are required to maintain > 80% power for the Clinically Significant Reintervention / Lesion Related Mortality Hypothesis. Assuming a 15% loss-to-follow-up rate, 102 subjects are sufficient for achieving the objective (with 81.48% power). For uncomplicated technical success, a sample size of 102 enrolled and implanted subjects (86 expected evaluable subjects) will yield a power of 93.41%. We expect the results of these hypotheses tests to be correlated, so an overall power calculation of the product of the two powers is inappropriate.

Expected accrual of subjects for the Primary Study Arm is 27 to 32 months.

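### Table 3 rules out surgical bypass for secondary patency but not for assisted primary patency, so a bypassed device that never occluded passes the stricter measure and fails the looser one

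*Combined protocol and SAP*

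**What the plan says.** SAP Section 2.3.2, Table 3, gives three patency measures, each labelled as an adapted study definition:

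- Primary patency: "Blood flow without occlusion maintained through the device after implant without an intervention".
- Assisted primary patency: "Blood flow maintained through the device after implant regardless of re-interventions performed (without occlusion".
- Secondary patency: "Blood flow through the device regardless of reinterventions performed (with or without occlusion) and freedom from surgical bypass".

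The Branch vessel patency row further down Table 3 has no definition of its own and refers to "Primary, Assisted Primary, Secondary Patency" at 12 months.

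Two other entries bear on how a bypass is scored. The All reinterventions row of Table 3 covers "An additional unanticipated interventional or surgical procedure (including conversion to open surgery), related to the device" or to the procedure, so an unanticipated, device-related surgical bypass is a reintervention. The Subject Safety row of Table 2, part of the second co-primary endpoint, lists "Total occlusion of a device component, use of a bypass graft or the performance of an open conversion" as alternatives, so the plan treats bypass and occlusion as separate events.

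**The concern.** The three definitions relax one condition at a time. Primary patency allows neither occlusion nor intervention, assisted primary allows intervention, and secondary also allows occlusion. A reader of the patency tables will expect every device that meets one measure to meet the next. The bypass exclusion runs the other way: it is a new restriction, and it appears only on the last and loosest step.

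At stake are the coherence of the aortic and branch patency tables and the meaning of assisted primary patency. If such a device occurs, the programmer must either report a contradictory pair of results or choose a rule after seeing the data.

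**Working it through.** The documents give no patency rate, goal or power, so there is no figure to reproduce. The check is on the logic of the definitions, followed by the arithmetic of the reported rates.

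**Step 1. Write the definitions as conditions.** Let F = flow through the device now, O = ever occluded, I = any intervention, B = surgical bypass.

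- Primary = F and not O and not I
- Assisted primary = F and not O
- Secondary = F and not B

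**Step 2. List the feasible device states.** Three constraints are assumed: a bypass counts as an intervention, absence of flow means the device has occluded, and reopening needs an intervention. Eight states remain.

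| Flow | Occluded | Intervention | Bypass | Primary | Assisted primary | Secondary |
|---|---|---|---|---|---|---|
| yes | no | no | no | yes | yes | yes |
| yes | no | yes | no | no | yes | yes |
| **yes** | **no** | **yes** | **yes** | **no** | **yes** | **no** |
| yes | yes | yes | no | no | no | yes |
| yes | yes | yes | yes | no | no | no |
| no | yes | no | no | no | no | no |
| no | yes | yes | no | no | no | no |
| no | yes | yes | yes | no | no | no |

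Exactly one state breaks the order: flow present, never occluded, bypassed. Primary ≤ assisted primary holds in all eight.

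**Step 3. Effect on the reported rates.** Let k be the number of devices in the bold state and m the number in the state below it (occluded, reopened, not bypassed). Only these two states score differently on the two measures, so

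secondary − assisted primary = (m − k)/N.

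Section 2.6 plans for "a sample size of 102 enrolled and implanted subjects (86 expected evaluable subjects" in the Primary Study Arm. These two sizes serve only to show scale, because Section 5.1 bases each secondary endpoint on the subjects evaluable for that variable. The values of k and m are assumptions. With one result per subject, in percentage points:

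| k | m | N = 86 | N = 102 |
|---|---|---|---|
| 0 | 0 | 0 | 0 |
| 1 | 0 | −1/86 = −1.2 | −1/102 = −1.0 |
| 3 | 0 | −3/86 = −3.5 | −3/102 = −2.9 |
| 1 | 1 | 0 | 0 |
| 1 | 2 | +1/86 = +1.2 | +1/102 = +1.0 |

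Per branch, assuming four branches per subject, N = 4 × 86 = 344. With m = 0, k = 1 to 3 then gives −1/344 = −0.3 to −3/344 = −0.9 points.

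**Step 4. Test the remedy.** Redefine assisted primary as F and not O and not B. The bold state becomes no/no/no, no state breaks the order, and the difference becomes m/N, which cannot be negative. With k = 1, m = 0 and no other occlusion at N = 86, the current wording gives assisted primary 86/86 = 100.0% and secondary 85/86 = 98.8%; after the change both are 98.8%. Dropping the bypass clause from secondary patency also restores the order, but then the fifth state (occluded, bypassed, flow present) becomes secondary patent.

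**The case against.** The strongest reply is that nothing in the documents says the measures are nested. These are adapted definitions, and a device with uninterrupted flow does what assisted primary patency describes. This stands in part: the nesting is inferred from the way the conditions relax. That inference is strong, however, and the plan offers no reason for the strictest bypass rule to sit on the loosest measure.

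A reader might infer more than the documents support:

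- **That every bypassed, never-occluded device is certainly misclassified.** The conflict needs flow to continue through the device after the bypass. If the device then occludes, both measures fail and agree. Calling the assisted primary result wrong also presupposes the nesting.
- **That assisted primary patency will be reported above secondary patency, or is biased upwards.** The rates reverse only if k exceeds m, and k may be zero. The documents do not say why an open device would be bypassed, or how often.
- **That Table 2 proves the error, because "use of a bypass graft or the performance of an open conversion in order to maintain bodily vessel function" is a co-primary event.** Total occlusion is a co-primary event too, yet a reopened device is secondary patent by design. Patency and clinically significant reintervention measure different things. Nor is the bypass hidden: it counts under Table 2 when done to maintain vessel function, and under All reinterventions when unanticipated and related to the device or procedure.

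A clarifying rule may also exist out of sight. Section 2.3.2 says most Table 3 definitions come from Clinical Protocol Section 3.3, which is not in the published text, and SAP Section 5.6 and parts of Sections 7 and 8 are redacted. The patency rows lack the asterisk that marks definitions made by the SAP itself, so the protocol probably carries the same wording. No visible text settles the case.

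**Conclusion.** The point holds as a defect of definition at device level: any k ≥ 1 produces a device that is assisted-primary patent and not secondary patent. It rests on the literal wording, the implied nesting, and flow persisting through the bypassed device.

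Its size is small and uncertain, since every count used above is assumed. Hypothesis tests are confined to the two co-primary endpoints (Sections 2.3.1 and 5.4), so study success, alpha, power and sample size do not change. This is a low-priority correction, best made before the data raise the question.

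**What to change.** Apply the same bypass condition to both measures. The preferred way is to add to assisted primary patency in Table 3 the clause on freedom from bypass that secondary patency already carries, and to make the same change in the protocol definition from which it is drawn. This also settles branch vessel patency, which reuses the measures.

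Add a programming check that primary ≤ assisted primary ≤ secondary for every device at every visit, with any exception listed for review.

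The cost is a short wording change in two documents that must stay aligned, plus one logic check. Assisted primary patency may come out slightly lower, by k/N.

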## 2.4 Statistical Hypotheses

The analysis of the Uncomplicated Technical Success / Procedural Safety endpoint is intended to test the hypothesis that the safety of the TAMBE Device exceeds the performance goal of 80% technical success. This analysis will be performed on the Primary Study Arm (pararenal aortic aneurysms and adapted Crawford Type IV TAAA). The analysis of the Clinically Significant Reintervention / Lesion Related Mortality endpoint is intended to test the hypothesis that the effectiveness of the TAMBE Device exceeds the performance goal of 68% free from clinically significant reintervention / lesion related mortality events.

The hypotheses are specified as follows:

Uncomplicated Technical Success / Procedural Safety Hypothesis:

$$H_0 : P_{UCT} \leq 0.80$$

$$H_A : P_{UCT} > 0.80$$

Where  $P_{UCT}$  denotes the proportion of subjects that achieve technical success.

Clinically Significant Reintervention / Lesion Related Mortality Hypothesis:

$$H_0 : P_{CSR} \leq 0.68$$

$$H_A : P_{CSR} > 0.68$$

Where  $P_{CSR}$  denotes the proportion of subjects that achieve freedom from clinically significant reintervention.

2.5

2.6 Sample Size Calculations

Sample size calculations were determined using PASS 13.0.8 (“Tests for One Proportion using Proportions” and “Exact” options).

The sample size calculation was motivated primarily by the Clinically Significant Reintervention Hypothesis / Lesion Related Mortality, since that would require more subjects to properly power than the Uncomplicated Technical Success / Procedural Safety hypothesis.

At least 86 are required to maintain > 80% power for the Clinically Significant Reintervention / Lesion Related Mortality Hypothesis. Assuming a 15% loss-to-follow-up rate, 102 subjects are sufficient for achieving the objective (with 81.48% power). For uncomplicated technical success, a sample size of 102 enrolled and implanted subjects (86 expected evaluable subjects) will yield a power of 93.41%. We expect the results of these hypotheses tests to be correlated, so an overall power calculation of the product of the two powers is inappropriate.

Expected accrual of subjects for the Primary Study Arm is 27 to 32 months.

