### 1.1 Study Success

Study success will be defined as rejecting the null hypotheses from both the Uncomplicated Technical Success Endpoint and the Clinically Significant Reintervention endpoints.

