#### 5.4 Statistical Analysis of Endpoints

One-sided exact Clopper-Pearson confidence intervals for binomial proportions ( $\alpha=0.05$ ) will be constructed to test the Uncomplicated Technical Success and Clinically Significant Reintervention hypotheses in the Primary Study Arm. The null hypothesis for each endpoint will be rejected if the lower bounds of the 95% confidence interval exceeds the corresponding performance goal. This is equivalent to stating that the estimated effectiveness and safety must exceed the PG with a Type I error rate ( $\alpha$ ) of  $< 0.05$ .

Primary and Secondary Endpoints will be summarized in the Secondary Study Arm, but no hypotheses tests will be performed.

All events must meet the protocol definition.

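### SAP Section 2.6 attaches 81.48% power to meeting the objective, but this is the power of one co-primary test; the power of the two-test success rule is not stated and is somewhat lower

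*Combined protocol and SAP*

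**What the plan says.** SAP Section 1.1 sets a conjunctive rule: "Study success will be defined as rejecting the null hypotheses from both the Uncomplicated Technical Success Endpoint and the Clinically Significant Reintervention endpoints". Section 2.1.1 likewise frames the primary objective as showing the device to be both safe and effective. Section 2.4 ties safety to the technical success / procedural safety endpoint, where the hypothesis is that the device "exceeds the performance goal of 80% technical success". It ties effectiveness to the 12-month endpoint, where the hypothesis is that the device "exceeds the performance goal of 68% free from clinically significant reintervention / lesion related mortality events".

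Section 2.6 sizes the trial on the 12-month endpoint, which needs at least 86 evaluable subjects for more than 80% power. It allows for 15% loss and concludes that "102 subjects are sufficient for achieving the objective (with 81.48% power"). It then reports 93.41% for technical success, also at 86 evaluable. It expects the two tests to be correlated, "so an overall power calculation of the product of the two powers is inappropriate", and gives no other overall figure.

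**The concern.** The only power that the section attaches to the objective belongs to one of two tests that must both succeed. Unless the two test outcomes are nested in a particular way, the chance of passing both is smaller than the chance of passing the harder one. Setting aside the product because of correlation leaves the success rule with no power figure, although correlation only moves the answer within limits that can be calculated.

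What is at stake is how a sponsor or regulator reads the design. Taken as the power for study success, 81.48% implies an 18.5% chance of missing it when the assumed rates are true (100 − 81.48). Type I error, the tests and the decision rule are not affected.

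**Working it through.** **Inputs**
- Tests: "One-sided exact Clopper-Pearson confidence intervals for binomial proportions" at 0.05 for each endpoint (SAP Section 5.4). "The null hypothesis for each endpoint will be rejected if the lower bounds of the 95% confidence interval exceeds the corresponding performance goal".
- Power method: the exact option of the PASS procedure "Tests for One Proportion using Proportions" (Section 2.6).
- Performance goals: 0.80 and 0.68 (Section 2.4).
- Evaluable subjects: 86 for each endpoint (Section 2.6). 86 / 0.85 = 101.2, rounded up to 102.
- True rates: not in the available text, because the content of Section 2.5 (Sample Size Assumptions) is absent. They are back-solved from the stated powers, which is an assumption.
- Correlation: expected by the plan but not quantified. The range taken runs from zero to the largest value that the rates allow.

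**Step 1: reproduce the stated powers.** For each test, find the smallest count c with P(X ≥ c | n = 86, goal) ≤ 0.05, then compute P(X ≥ c | n = 86, true rate).
- 12-month endpoint, goal 0.68: c = 66, so at most 20 failures. Actual alpha is 0.0494. At a true rate of 0.80 the power is 0.8148, the stated 81.48%.
- Technical success, goal 0.80: c = 76, so at most 10 failures. Actual alpha is 0.0298. At a true rate of 0.923 the power is 0.9341, the stated 93.41%.

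Both are single-endpoint powers and both are right.

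**Step 2: bounds that need no true rates.** The joint power cannot exceed the smaller single power, 81.48%. Under independence it is 0.8148 × 0.9341 = 0.7611. With no assumption on dependence at all, it is at least 0.8148 + 0.9341 − 1 = 0.7489.

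**Step 3: joint power under positive correlation.** Let q1 = 0.077 and q2 = 0.20 be the failure rates for technical success and the 12-month endpoint. For within-subject correlation φ, the probability that a subject fails both is

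b = q1·q2 + φ·√(q1(1 − q1)·q2(1 − q2)) = 0.0154 + 0.1066·φ.

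Since b cannot exceed q1 = 0.077, the largest φ is (0.077 − 0.0154) / 0.1066 = 0.578. There, every technical-success failure is also a 12-month failure. Given k technical-success failures among 86, the number of 12-month failures is Bin(k, b/q1) + Bin(86 − k, (q2 − b)/(1 − q1)). Joint power is the sum over k = 0 to 10 of P(k) × P(12-month failures ≤ 20 | k).

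**Step 4: more subjects evaluable at 30 days.** Population 3 in Section 5.1 needs only a visit at or after day 30, or an event, so all 102 might count for technical success. The pass mark is then 89 of 102 and the single power is 97.5%. The 16 extra subjects enter that test only.

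| φ | b | Joint power, 86 and 86 | Joint power, 102 (30-day) and 86 (12-month) |
|---|---|---|---|
| 0 | 0.0154 | 76.1% | 79.5% |
| 0.2 | 0.0367 | 77.0% | 79.8% |
| 0.4 | 0.0581 | 78.0% | 80.3% |
| 0.578 (maximum) | 0.0770 | 79.1% | 80.7% |

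Simulation with 1,000,000 replicates gives 76.1% and 79.1% at the two ends of the 86-and-86 column. The ceiling of 81.48% is not reached in either column. With 86 for each, the chance of missing study success is 20.9% to 23.9%.

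**Step 5: sensitivity to the evaluable count.** With 87 evaluable for each (102 × 0.85 = 86.7), the 12-month power is 79.9% and the joint power 74.3% to 77.5%. With all 102 evaluable for both, the joint power is 82.4% to 83.8%, but that contradicts the plan's 15% loss.

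**The case against.** The strongest reply is that Section 2.6 never presents 81.48% as the power of the study. The sentence just before it sets the target of more than 80% for the reintervention / lesion-related mortality hypothesis, so the objective may mean only that target. The next sentence gives technical success its own figure, and the closing sentence treats overall power as something separate. This reading is plausible and cannot be excluded. It does not remove the point: Section 2.1.1 uses the same word for safety and effectiveness together, and on either reading Section 2.6 gives no power for the rule in Section 1.1.

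Four stronger conclusions that a reader might draw are not supported.
- *The design falls short of its own power target.* The visible plan sets more than 80% for the 12-month hypothesis only, and 81.48% meets it. No joint target is stated.
- *Joint power is below 80% whatever happens.* That holds with 86 evaluable for both endpoints. With 102 for the 30-day endpoint, the range straddles 80%.
- *The arithmetic in Section 2.6 is wrong.* Its powers and its sample size all reproduce.
- *The remark about the product is mistaken.* The product is not the exact joint power when the tests are correlated, and the plan says no more than that. It does not say that joint power cannot be computed.

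It is also fair to object that the true rates are inferred and that Section 2.5 might address rates, correlation or overall power. Both rates match the stated powers to four digits, but they remain an inference. The 81.48% ceiling and the 76.1% product do not depend on them.

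**Conclusion.** The point stands as an omission and a loose label. The figure attached to the objective is a single-test power, while study success needs two rejections. The shortfall against 81.48% is about 2 to 5 percentage points with 86 evaluable for each endpoint (81.48 − 79.1 = 2.4; 81.48 − 76.1 = 5.4). It is about 1 to 2 points if all 102 are evaluable at 30 days (81.48 − 80.7 = 0.8; 81.48 − 79.5 = 2.0). These sizes rest on the back-solved rates of 80% and 92.3%, non-negative within-subject correlation, and 86 evaluable at 12 months. The correction is worth making because the study is confirmatory and its success rule is conjunctive, but it concerns reporting and not the validity of the design.

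**What to change.** In SAP Section 2.6:

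1. Label 81.48% as the power for the reintervention / lesion-related mortality hypothesis alone.
2. Keep the remark that the product is not exact under correlation. Add that under non-negative correlation the product, about 76%, is a lower value for the joint power.
3. State the power for study success with its assumptions. For example: *With true rates of 80% and 92.3%, the power to reject both null hypotheses is about 76% (independent endpoints) to 79% (strongest possible positive within-subject correlation) if 86 subjects are evaluable for each endpoint, and about 79.5% to 81% if all 102 are evaluable for the 30-day endpoint.* The sponsor should replace the rates with those in Section 2.5 if they differ.

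The cost is a few sentences and a slightly less favourable stated figure. Sample size, endpoints, tests and decision rule stay as they are.
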